1. BACKGROUND INFORMATION

1.1 Indication and Current Treatment Options

Conjunctivitis affects all populations worldwide of all ages and social strata, irrespective of gender. Within infectious conjunctivitis, viral etiology may account for up to 80% of all cases in adults and bacterial conjunctivitis is the second most common cause of infectious conjunctivitis overall. Infectious conjunctivitis represents a serious public health issue due to a risk of highly infectious epidemics, lost productivity, significant patient discomfort, and in some cases permanent visual compromise from long-term, immune-mediated sequelae (Ford et al., 1987; Nauheim et al., 1990; Gordon et al., 1993; Pelletier et al., 2009; Capriotti et al., 2010).

Adenoviruses, unlike bacteria, are not part of the normal flora of the ocular surface and their presence is indicative of an infection (Cambon and Pollard, 1959; Williamson et al., 1975; Vastine et al., 1977; Gigliotti et al., 1981; Kaneko et al., 2008). It is the most reported cause of viral conjunctivitis in up to 75% of cases (Wilkins et al., 2011). Adenoviral conjunctivitis is typically spread through direct contact between the eye and hands that are contaminated with the virus via contact with infected eye discharge, fecal matter, or respiratory discharge (CDC, 2010). Given the highly transmittable nature of the disease, it is not surprising that it is observed to be most prevalent in densely populated, overcrowded areas, or in the presence of poor hygiene, or both (Capriotti et al., 2010).

Adenoviral conjunctivitis typically lasts 14-21 days (Wilkins et al., 2011). The onset is usually rapid and the infection often spreads from one eye to the other (AAO Cornea/External Disease PPP Panel, 2013).

Currently, there are no approved treatments for adenoviral conjunctivitis; therapeutic options are limited to supportive therapies and palliative measures such as cold compresses, artificial tears, and topical antihistamines (AAO Cornea/External Disease PPP Panel, 2013). This Phase 3 study is being conducted to evaluate the clinical efficacy and safety of SHP640 for the treatment of adenoviral conjunctivitis.

1.2 Product Background and Clinical Information

SHP640, a novel topical ophthalmic suspension, is currently under development for the treatment of infectious conjunctivitis (adenoviral and bacterial).

SHP640 contains 2 active ingredients: povidone-iodine (PVP-I) and dexamethasone. PVP-I is a multivalent broad-spectrum local antiseptic with bactericidal and fungicidal properties. The effect on vegetative cells of various bacteria and fungi is due to the liberation of free iodine from the complex. It is effective against many viruses, protozoa, yeasts, cysts, and spores (Betadine, 2004). Dexamethasone is a corticosteroid routinely used as a topical ophthalmic suspension for the treatment of ocular inflammation. It suppresses the inflammatory response to a variety of causes of inflammation (Maxidex, 2007). Both components are currently approved for use in other indications (at similar or higher concentrations) and have been shown to be safe and efficacious for use on the ocular surface in humans.

The combination of PVP-I and dexamethasone has been shown to rapidly kill common ocular pathogens, including viruses, gram-positive bacteria (including MRSA), and gram-negative bacteria ([Pelletier et al., 2011](#)).

Always refer to the latest version of the SHP640 investigator's brochure for the overall risk/benefit assessment and the most accurate and current information regarding the drug metabolism, pharmacokinetics, efficacy and safety of SHP640.

2. STUDY OBJECTIVES AND PURPOSE

2.1 Rationale for the Study

The clinical presentation of conjunctivitis is often nonspecific and differential diagnosis of different types of conjunctivitis can be challenging (Azari and Barney, 2013; O'Brien et al., 2009). Diagnostic testing to differentiate the underlying cause of infection is rarely performed in a clinical setting; misdiagnosis can occur in up to 50% of cases, which often results in improper antibiotic treatment (Visscher et al., 2009). Incorrect treatment can not only increase healthcare costs from unnecessary antibiotic prescriptions and repeat office visits, but can also pose serious risks for people with certain viral and bacterial variants (eg, herpes simplex or methicillin-resistant *Staphylococcus aureus* [MRSA]). In addition, there is also a risk of overuse and misuse of antibiotics, which are ineffective in the treatment of viral infections (Statham et al., 2008). Currently there is no approved medication for the treatment of adenoviral conjunctivitis. An unmet medical need therefore exists for a safe and efficacious treatment that addresses both bacterial and adenoviral conjunctivitis, two of the leading causes of acute infectious conjunctivitis.

By combining PVP-I, a potent topical antiseptic with proven antiviral and antibacterial activity, with dexamethasone, a topical steroid, SHP640 will enable the treatment of both the infectious and inflammatory components of adenoviral and bacterial conjunctivitis.

2.2 Study Objectives

2.2.1 Primary Objective

The primary objective of this study is to evaluate the efficacy of SHP640 based on clinical resolution (defined as absence of bulbar conjunctival injection and watery conjunctival discharge) compared with placebo in the treatment of subjects with adenoviral conjunctivitis in the study eye at Visit 3 (Day 6).

2.2.2 Key Secondary Objectives

Key secondary objectives of this study are as follows:

- To evaluate the efficacy of SHP640 based on clinical resolution compared with PVP-I in the treatment of subjects with adenoviral conjunctivitis in the study eye at Visit 3 (Day 6).
- To evaluate the efficacy of PVP-I based on adenoviral eradication (defined as negative cell culture-immunofluorescence assay [CC-IFA]) compared with placebo in the treatment of subjects with adenoviral conjunctivitis in the study eye at Visit 2 (Day 3).
- To evaluate the efficacy of SHP640 based on adenoviral eradication compared with placebo in the treatment of subjects with adenoviral conjunctivitis in the study eye at Visit 3 (Day 6).
- To evaluate the efficacy of SHP640 based on adenoviral eradication compared with PVP-I in the treatment of subjects with adenoviral conjunctivitis in the study eye at Visit 3 (Day 6).
- To evaluate the efficacy of PVP-I based on clinical resolution compared with placebo in the treatment of subjects with adenoviral conjunctivitis in the study eye at Visit 3 (Day 6).

Adenoviral eradication is defined in Section 7.2.2.

[figure not shown]
2.2.3 Secondary Objectives

Secondary objectives of this study are as follows:

- To evaluate the effect of treatment in the study eye, for the following endpoints:
 - Adenovirus viral titer assessed by quantitative polymerase chain reaction (qPCR) at Visit 3 (Day 6) and 4 (Day 8)
 - Adenoviral eradication as assessed by CC-IFA at Visits 4 (Day 8) and 5 (Day 12)
 - Clinical resolution of adenoviral conjunctivitis at Visits 2 (Day 3), 4 (Day 8) and 5 (Day 12)
 - Individual clinical signs (bulbar conjunctival injection and watery conjunctival discharge) at Visits 2 (Day 3), 3 (Day 6), 4 (Day 8) and 5 (Day 12)
 - The global clinical score (sum of bulbar conjunctival injection and watery conjunctival discharge) and change from baseline in the global clinical score at Visits 2 (Day 3), 3 (Day 6), 4 (Day 8) and 5 (Day 12).
 - Modified clinical resolution, defined as a global clinical score of 0 or 1, at Visits 2 (Day 3), 3 (Day 6), 4 (Day 8) and 5 (Day 12)
 - Expanded clinical resolution, defined as a global clinical score of 0, 1, or 2 with neither injection nor discharge having a score of 2, at Visits 2 (Day 3), 3 (Day 6), 4 (Day 8) and 5 (Day 12)
 - Time to clinical resolution based upon assessments at Visits 2 (Day 3), 3 (Day 6), 4 (Day 8), and 5 (Day 12)
- To assess the status of cross-over infection (as assessed by CC-IFA) to a subject's fellow eye at Visits 2 (Day 3), 3 (Day 6), 4 (Day 8) and 5 (Day 12) for subjects with only 1 infected eye at baseline
- To evaluate the safety and tolerability of SHP640, compared to PVP-I and placebo in the treatment of subjects with adenoviral conjunctivitis

2.2.4 Exploratory Objectives

The exploratory objectives of this study are as follows:

3. STUDY DESIGN

3.1 Study Design and Flow Chart

SHP640-301 is a global, multi-center, randomized, double-masked, parallel group, placebo controlled study designed to demonstrate the safety and efficacy of SHP640 ophthalmic suspension compared to PVP-I 0.6% ophthalmic solution and to placebo in treating adenoviral conjunctivitis.

[figure not shown]
Approximately 930 subjects will be randomized into the study at Visit 1 (Day 1). Subjects will be randomized 2:2:1 to receive either SHP640, PVP-I, or placebo within each stratum. Randomization will be stratified by age to maintain the randomization ratio among subjects < 6 years, 6 to <18 years and subjects ≥ 18 years.

Multiple subjects from the same household will be eligible to participate in the study. Subjects from the same household will be assigned to the same treatment group to which the first enrolled subject in the household was randomized in order to prevent treatment administration errors or potential treatment unmasking. Dynamic balanced randomization will be used in this study to maintain the randomization ratio within each stratum.

Once screening and baseline assessments are complete and subjects are confirmed eligible to enroll in the study, subjects will be randomized, and investigational product will be administered on the same day (Day 1). The first dose will be administered by site staff on Day 1, and thereafter subjects will administer 1 drop in each eye 4 times a day (QID) for 7 days. Additional visits will occur on Visit 2 (Day 3), Visit 3 (Day 6), Visit 4 (Day 8), and Visit 5 (Day 12). All follow-up procedures will be conducted at Visit 5 (Day 12). The study will last up to 13 days.

Figure 1 provides the study design.

Figure 1 SHP640-301 Study Design

3.2 Duration and Study Completion Definition

The subject's maximum duration of participation is expected to be approximately 13 days. The study will be completed in approximately 1.5 years.

The Study Completion Date is defined as the date the final subject, across all sites, completes their final protocol-defined assessment. Please note that this includes the follow-up visit (Visit 5) or contact, whichever is later. The Study Completion Date is used to ascertain timing for study results posting and reporting.

3.3 Sites and Regions

The study will be conducted in approximately 100 sites across North America, South America, Asia/Pacific, Europe, the Middle East, and Africa.

4. STUDY POPULATION

Each subject must participate in the informed consent process and provide written informed consent before any procedures specified in the protocol are performed. If a subject is younger than the legal age of consent (per local laws), the subject's parent(s), guardian, or legally authorized representative will provide written informed consent; the subject will provide verbal or written assent as appropriate.

4.1 Inclusion Criteria

The subject will not be considered eligible for the study without meeting all of the criteria below.

1. An understanding, ability, and willingness to fully comply with study procedures and restrictions (by the parent(s), guardian, or legally authorized representative, if applicable).
2. Ability to voluntarily provide written, signed, and dated (personally or via a parent(s), guardian, or legally-authorized representative(s) informed consent (and assent, if applicable) to participate in the study.
3. Subjects of any age at Visit 1 (Note: subjects < 3 months of age at Visit 1 must have been full-term, ie ≥ 37 weeks gestational age at birth).
4. Have a positive AdenoPlus® test at Visit 1 in at least 1 eye.
5. Have a clinical diagnosis of suspected adenoviral conjunctivitis in at least 1 eye (the same eye as the AdenoPlus positive eye) confirmed by the presence of the following minimal clinical signs and symptoms in that same eye:
 - Report presence of signs and/or symptoms of adenoviral conjunctivitis for ≤ 4 days prior to Visit 1
 - Bulbar conjunctival injection: a grade of ≥ 1 on 0-4 scale of Bulbar Conjunctival Injection Scale
 - Watery conjunctival discharge: a grade of ≥ 1 (mild) on a 0-3 Watery Conjunctival Discharge Scale
6. Be willing to discontinue contact lens wear for the duration of the study.
7. Have a Best Corrected Visual Acuity (BCVA) of 0.60 logMAR or better in each eye as measured using an Early Treatment Diabetic Retinopathy Study (ETDRS) chart. BCVA will be assessed by an age appropriate method in accordance with the AAP Policy Statement for Visual System Assessment in Infants, Children, and Young Adults by Pediatricians ([Donahue and Baker, 2016](#); [American Academy of Pediatrics, 2016](#)). The policy statement recommends formal vision screening can begin at 3 years of age. VA measurements for children under the age of 3 will be done at the discretion of the investigator. If not done, child should be able to fixate on and follow a moving object, except subjects <2 months of age who have not yet developed this ability. Subjects <2 months will be enrolled at the discretion of the investigator.
8. Male, or non-pregnant, non-lactating female who agrees to comply with any applicable contraceptive requirements of the protocol or females of non-childbearing potential.

4.2 Exclusion Criteria

Subjects are excluded from the study if any of the following exclusion criteria are met.

1. Current or recurrent disease that could affect the action, absorption, or disposition of the investigational product, or clinical or laboratory assessments, per investigator's discretion.
2. Current or relevant history of physical or psychiatric illness, any medical disorder that may make the subject unlikely to fully complete the study, or any condition that presents undue risk from the investigational product or procedures.
3. Have known or suspected intolerance or hypersensitivity to the investigational product, closely related compounds, or any of the stated ingredients.
4. Prior enrollment in a FST-100 or SHP640 clinical study.
5. Subjects who are employees, or immediate family members of employees (who are directly related to study conduct), at the investigational site.
6. Have a history of ocular surgical intervention within ≤ 6 months prior to Visit 1 or planned for the period of the study.
7. Have a preplanned overnight hospitalization during the period of the study.
8. Have presence of any intraocular, corneal, or conjunctival ocular inflammation (eg, uveitis, iritis, ulcerative keratitis, chronic blepharoconjunctivitis), other than adenoviral conjunctivitis.
9. Have presence of corneal subepithelial infiltrates at Visit 1.
10. Have active or history of ocular herpes.
11. Have at enrollment or within ≤ 30 days of Visit 1, a clinical presentation more consistent with the diagnosis of non-infectious conjunctivitis (except presumed seasonal/perennial allergic conjunctivitis) or non-adenoviral ocular infection (eg, bacterial, fungal, acanthamoebal, or other parasitic). Note: history or concomitant presence of presumed seasonal or perennial allergic conjunctivitis signs/symptoms is not exclusionary.
12. Neonates or infants (ie, subjects less than 12 months of age) who have suspected or confirmed (based on the result of any test conducted prior to screening) conjunctivitis of gonococcal, chlamydial, herpetic or chemical origin.
13. Neonates or infants (ie, subjects less than 12 months of age) whose birth mothers had any sexually transmitted disease within 1 month of delivery or any history of genital herpes.
14. Presence of nasolacrimal duct obstruction at Visit 1 (Day 1).
15. Presence of any significant ophthalmic condition (eg, Retinopathy of Prematurity, congenital cataract, congenital glaucoma) or other congenital disorder with ophthalmic involvement that could affect study variables.
16. Be a known intraocular pressure (IOP) steroid responder, have a known history or current diagnosis of glaucoma, or be a glaucoma suspect.
17. Have any known clinically significant optic nerve defects.

18. Have a history of recurrent corneal erosion syndrome, either idiopathic or secondary to previous corneal trauma or dry eye syndrome; presence of corneal epithelial defect or any significant corneal opacity at Visit 1.
19. Presence of significant, active condition in the posterior segment which requires invasive treatment (eg, intravitreal treatment with VEGF inhibitors or corticosteroids) and may progress during the study participation period.
20. Have used any topical ocular or systemic anti-virals or antibiotics within ≤ 7 days of enrollment.
21. Have used any topical ocular NSAIDs within ≤ 1 day of enrollment.
22. Have used any topical ophthalmic steroids in the last ≤ 14 days.
23. Have used any systemic corticosteroid agents within ≤ 14 days of Day 1. Stable (initiated ≥ 30 days prior to enrollment) use of inhaled and nasal corticosteroids is allowed, given no anticipated change in dose for the duration of the study. Topical dermal steroids are allowed except in the peri-ocular area.
24. Have used non-corticosteroid immunosuppressive agents within ≤ 14 days of Day 1.
25. Have used any topical ophthalmic products, including tear substitutes, and over-the-counter preparations such as lid scrubs, within 2 hours of Visit 1 and be unable to discontinue all topical ophthalmic products for the duration of the study. Use of hot or cold compresses is also not permitted during the study.
26. Have any significant ocular disease (eg, Sjogren's syndrome) or any uncontrolled systemic disease or debilitating disease (eg, cardiovascular disease, hypertension, sexually transmitted diseases/infections, diabetes or cystic fibrosis), that may affect the study parameters, per investigator's discretion.
27. Any known history of immunodeficiency disorder or known active conditions predisposing to immunodeficiency, such as human immunodeficiency virus, hepatitis B or C, evidence of active hepatitis A (antihepatitis A virus immunoglobulin M), or organ or bone marrow transplantation.
28. Within 30 days prior to the first dose of investigational product:
 - Have used an investigational product or device, or
 - Have been enrolled in a clinical study (including vaccine studies) that, in the investigator's opinion, may impact this Shire-sponsored study

4.3 Reproductive Potential

4.3.1 Female Contraception

Sexually active females of childbearing potential should be using an acceptable form of contraception throughout the study period. If hormonal contraceptives are used, they should be administered according to the package insert. Females of childbearing potential who are not currently sexually active must agree to use acceptable contraception, as defined below, if they become sexually active during the period of the study.

Female children and adolescent subjects should be either:

- Pre-menarchal and either Tanner Stage 1 or less than age 9 years, or
- Females of childbearing potential with a negative urine pregnancy test at Visit 1. Females of childbearing potential must agree to abstain from sexual activity that could result in pregnancy or agree to use acceptable methods of contraception.

Adult female subjects should be either:

- Postmenopausal (12 consecutive months of spontaneous amenorrhea and \geq age 51 years)
- Surgically sterile (having undergone one of the following surgical acts: hysterectomy, bilateral tubal ligation, bilateral oophorectomy or bilateral salpingectomy) and at least 6 weeks post-sterilization, or
- Females of childbearing potential with a negative urine pregnancy test at Visit 1 and prior to randomization. Females of childbearing potential must agree to abstain from sexual activity that could result in pregnancy or agree to use acceptable methods of contraception.

Acceptable methods of contraception are:

- Intrauterine devices plus condoms
- Intrauterine hormone-releasing systems plus condoms
- Double-barrier methods (eg, condoms and diaphragms with spermicidal gel or foam)
- Hormonal contraceptives (oral, depot, patch, injectable, or vaginal ring), stabilized for at least 30 days prior to the screening visit (Visit 1), plus condoms.

4.4 Discontinuation of Subjects

A subject may withdraw from the study at any time for any reason without prejudice to their future medical care by the physician or at the institution. The investigator or sponsor may withdraw the subject at any time (eg, if in the judgment of the investigator, there is no clinical improvement or worsening to an extent that it would be in the best interest of the subject to be treated with an alternate therapy for safety reasons). The investigator is encouraged to discuss withdrawal of a subject from investigational product with the medical monitor if necessary.

If investigational product is discontinued for any reason other than a positive HSV baseline test, the evaluations listed for Visit 5 are to be performed as completely as possible. Whenever possible, all discontinued subjects should also undergo the protocol-specified follow-up (proceed to Visit 5). Comments (spontaneous or elicited) or complaints made by the subject must be recorded in the source documents. The reason for termination and the date of stopping investigational product must be recorded in the case report form (CRF) and source documents.

Subjects who test positive for ocular HSV at baseline in either eye should have their investigational product discontinued, and should receive alternate appropriate treatment as needed based on the investigator's judgment. These subjects should be followed for the remaining duration of study at regularly scheduled visits, and all safety related assessments should be completed (AEs, BCVA, slit lamp biomicroscopy at all visits [fundus exam at Visit 5], concomitant medications at all visits, and pregnancy test [if the subject is a female of childbearing potential]).

If a subject <2 months of age has a positive CT-NG test for any one of the two Visit 1 samples, the subject will be discontinued from the study and started with alternate standard of care therapy per the investigator's clinical judgment.

Subject numbers for subjects who discontinue will not be reused.

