| Watery conjunctival discharge evaluation | X | X | X | X | X |
| AdenoPlus [®] test | X ^d | | | | |
| Conjunctival swab for viral culture ^e | X ^m | X ^f | X ^f | X ^f | X ^f |
| Conjunctival swab for bacterial culture ^e | X | | X ^{f,g} | | X ^f |
| Non-dilated/ dilated fundus examination ^h | X | | | | X |
| Randomization ⁱ | X | | | | |
| Dispense investigational product ^j | X | | | | |
| Instill investigational product | X ^j | X ^k | X ^k | | |
| Collect investigational product | | | | X | X ^b |
| Compliance assessment | | X | X | X | X ^b |
| Drug accountability | | | | X | X ^b |

Table 1 Schedule of Assessments

| Procedure (All ocular assessments and procedures performed bilaterally) | Visit 1 Screening^a & Baseline (Day 1) -1 Day | Visit 2 (Day 3) +1 Day | Visit 3 (Day 6) | Visit 4 (Day 8) +1 Day | Visit 5^b (Day 12) +2 Days |
|--|--|---------------------------------------|----------------------------|---------------------------------------|---|
| Adverse events | X ^l | X | X | X | X |
| Study completion | | | | | X |

CC-IFA= cell culture-immunofluorescence assay; HSV= herpes simplex virus; qPCR= quantitative polymerase chain reaction;

^a Informed consent and confirmation of inclusion/exclusion criteria can be conducted on Day -1; Inclusion/Exclusion must be re-confirmed on Day 1.

^b If investigational product is discontinued, regardless of the reason, all discontinued subjects should proceed to Visit 5 whenever possible. Subjects that discontinue the study and proceed to Visit 5 should perform all Visit 5 assessments as well as drug return, compliance and accountability.

^c Women of childbearing potential, prior to enrollment and at exit from the study.

^d If not previously conducted within 24 hours of Visit 1 (Day 1)

^e One swab sample from inferior conjunctival cul-de-sac of each eye will be collected for all viral testing. If the CC-IFA test is positive, qPCR will be performed. Adenoviral serotyping will be conducted at baseline only.

^f Conjunctival swab samples MUST be taken at least 12 hours after the last dose of investigational product at Visits 2, 3, 4 and ET, if applicable.

^g One swab sample from each conjunctival cul-de-sac will be collected for all bacterial testing.

^h If a non-dilated fundus exam is not feasible, a dilated examination should be conducted. For each subject, the exam should be conducted the same way (either non-dilated or dilated) at both Visit 1 and Visit 5 (or ET).

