6.2.4 Unmasking the Treatment Assignment

The treatment assignment must not be broken during the study except in emergency situations where the identification of the investigational product is required for further treatment of the subject. The investigator should contact the medical monitor as soon as possible after the unmasking occurs.

In the event that the treatment assignment is broken, the date and person who broke the code will be recorded by the IRT and the reason for breaking will be recorded on the CRF. Upon breaking the mask, the subject is withdrawn from the study, but should complete Visit 5 (the end of study visit), to be followed up for safety purposes. Any code-breaks that occur must be reported to the Sponsor medical monitor.

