7.1.3 Visit 5 (End of Study or Early Termination)

Safety follow-up will be conducted at Visit 5 (the end of study visit). Visit 5 (Day 12 [+2 days]) assessments will be performed as outlined in [Table 1](#). Assessments should be performed in descending order as listed.

Subjects who discontinue the study and proceed to Visit 5 for early termination should have investigational product collected, a compliance assessment, and drug accountability assessed at their final visit.

All AEs and SAEs that are not resolved at the time of Visit 5 or early termination will be followed to closure (see [Section 8.1](#)).

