9.6 Sample Size Calculation and Power Considerations

The sample size was estimated for the primary comparison and key secondary comparisons of SHP640 Ophthalmic Suspension to Placebo and to PVP-I by using nQuery Advisor 7.0. Subjects will be randomized 2:2:1 ratio to receive either SHP640 ophthalmic suspension, PVP-Iodine 0.6%, or placebo within each stratum.

A sample size of 350 subjects (140 subjects in each of SHP640 and PVP-I groups, 70 subjects in placebo) will ensure 90% power to compare the SHP640 and Placebo treatment groups assuming 31% and 11% subjects with clinical resolution respectively using Fisher's Exact test at two-sided 5% level of significance.

However, a sample size of 605 subjects (242 subjects in each of SHP640 and PVP-I groups, 121 subjects in placebo) will ensure 90% power to compare SHP640 and PVP-I treatment groups assuming 31% and 18% subjects with clinical resolution respectively using Fisher's Exact test at two-sided 5% level of significance.

Therefore, 605 subjects will ensure 90% power for testing the hypothesis corresponding to the key secondary objective of comparing clinical resolution status in SHP640 vs PVP-I.

The assumed proportions of subjects with clinical resolution in the 3 treatment arms are based on response rates observed in FST100-AVC-004 with a dropout rate of approximately 6% prior to Visit 3 in FST100-AVC-004 mITT population which excluded subjects with no post baseline data. The dropout rate would become approximately 8% if FST100-AVC-004 mITT population included subjects with no post baseline data.

All efficacy analyses will be based on the mITT population with post-baseline LOCF for the subjects with missing clinical resolution status at Visit 3 (Day 6). To ensure 605 subjects in the mITT population, approximately 930 subjects will be randomized in this study (approximately 372 subjects in each of SHP640 and PVP-I groups, approximately 186 subjects in placebo).

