9.8.2 Primary Efficacy Endpoint

The primary efficacy endpoint is clinical resolution status (defined as absence [ie a score of 0] of bulbar conjunctival injection and watery conjunctival discharge) in the study eye at Visit 3 (Day 6) between SHP640 and placebo.

All efficacy analyses will be performed on the mITT and presented by treatment groups. There is a single primary comparison for the single primary endpoint. Therefore, no adjustment of multiplicity is needed for the hypothesis testing for the primary objective.

The primary efficacy endpoint of clinical resolution in the study eye at Visit 3 (Day 6) will be compared between the SHP640 and placebo group. The comparison will be based on the proportion of subjects with clinical resolution in the study eye at Visit 3 (Day 6) using Fisher's Exact test at two sided 0.05 significance level.

If subjects have missing clinical resolution status at Visit 3 (Day 6), then the last post-baseline observation will be carried forward (LOCF) for the determination of clinical resolution of the study eye.

The null hypothesis to be tested is that there is no difference in proportion of subjects with clinical resolution in the study eye between SHP640 Ophthalmic Solution and Placebo with the alternative of the non-zero difference in the proportion with clinical resolution between them.

The proportion of subjects with clinical resolution will be compared with two-sided Fisher's Exact test at 5% level of significance.

Sensitivity analyses will be done on the primary efficacy endpoint using additional statistical method(s) including other methods of imputation of missing data. Sensitivity analyses may be conducted in the ITT in addition to the mITT. In addition, descriptive statistics will be generated for the primary efficacy endpoint by treatment within the overall pediatric population (ie birth to 18 years) and within each pediatric age stratum (birth to <6 years and 6 to <18 years) in mITT. A detailed plan for primary analysis including additional sensitivity analyses will be described in the Statistical Analysis Plan (SAP).

[figure not shown]

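### Subjects who stop product or are unmasked are directed to the Visit 5 exit assessment with no request for Visit 3 scoring, so those who stop before Day 6 will usually have no Day 6 endpoint value

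*Protocol*

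**What the plan says.** The primary endpoint is clinical resolution "in the study eye at Visit 3 (Day 6) between SHP640 and placebo" (Protocol 9.8.2). Four of the five key secondary comparisons in 9.8.3 are also read at Visit 3.

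For subjects who leave treatment early, the documents give these instructions:

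- Protocol 4.4: if product is stopped for any reason except a positive baseline HSV test, "the evaluations listed for Visit 5 are to be performed as completely as possible". It adds: "Whenever possible, all discontinued subjects should also undergo the protocol-specified follow-up (proceed to Visit 5".
- Protocol Table 1, footnote b: "If investigational product is discontinued, regardless of the reason, all discontinued subjects should proceed to Visit 5 whenever possible".
- Protocol 7.1.3, whose heading covers both end of study and early termination: "Subjects who discontinue the study and proceed to Visit 5 for early termination should have investigational product collected". It calls this their final visit.
- Protocol 6.2.4: "Upon breaking the mask, the subject is withdrawn from the study, but should complete Visit 5 (the end of study visit".
- SAP 2.3 and footnote b of the SAP's Table 1 repeat the unmasking and discontinuation rules.

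One group is treated differently. Under 4.4, HSV-positive subjects stop product but stay on the regular visits. Only safety assessments are listed for them, without injection and discharge grading or a swab.

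On missing data, Protocol 9.8.2 states: "If subjects have missing clinical resolution status at Visit 3 (Day 6), then the last post-baseline observation will be carried forward (LOCF". The same section commits to sensitivity analyses with other imputation methods, and 9.8.3 extends this to the key secondary endpoints. The SAP has no LOCF rule. SAP 18.3 sets resolution to missing when either score is missing, and SAP 18.2 tabulates by CRF visit. SAP 2.6, 10.2 and 17 drop all hypothesis testing because the study was terminated early.

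**The concern.** Stopping product is handled as leaving the visit schedule. Someone who stops on Day 3 or 4 is asked for the exit evaluations, and no section asks for Visit 3 scoring as well. In a trial read at Visit 3, that leaves a gap which depends on outcome: 4.4 names lack of improvement and worsening as reasons for withdrawal, and 4.4.1 lists lack of efficacy and adverse events. Stopping rates may also differ between an iodine and steroid combination, iodine alone and placebo.

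Analysis by assigned treatment (SAP 4.4 and 10) needs outcomes whether or not product was continued. Here the follow-up rule works against the analysis rule, although the missing visit is already in the schedule. At stake is whether the Day 6 proportions describe everyone in the arm or only those who were still attending.

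**Working it through.** **1. Is Visit 3 requested anywhere after stopping?** Protocol 4.4, 6.2.4, 7.1.3 and Table 1 footnote b all name Visit 5 and no other visit. The HSV exception in 4.4 keeps the visits but not the efficacy assessments. So no group that stops product before Day 6 has a stated request for the Day 6 endpoint. Footnote b applies whatever the reason, whereas 4.4 exempts HSV-positive subjects; these two passages must be reconciled.

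**2. Does the exit visit supply a Day 6 value?** Visit 5 includes both grades and a viral swab, so data exist. The documents do not fix the date of an early exit visit. Under SAP 18.2 it stays labelled Visit 5, and no rule maps it to Visit 3.

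**3. The plan's own figures.** Exact power of the two-sided 5% Fisher test, by full enumeration:

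- 140 vs 70, 31% vs 11%: 91.8% (stated 90%)
- 242 vs 242, 31% vs 18%: 90.2% (stated 90%)

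For randomized numbers, 605/0.65 = 930.8 (stated 930) and 350/0.65 = 538.5 (stated 540). No planned figure is wrong, and the point does not rest on one.

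**4. How many subjects?** Protocol 9.6 and SAP 2.5 cite, from the earlier study, "a dropout rate of approximately 6% prior to Visit 3" when subjects without post-baseline data are excluded, and about 8% when they are included.

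| mITT size | 6% | 8% |
|---|---|---|
| 605 (Protocol) | 36.3 | 48.4 |
| 242 per active arm | 14.5 | 19.4 |
| 121 placebo | 7.3 | 9.7 |
| 350 (SAP) | 21.0 | 28.0 |
| 140 per active arm | 8.4 | 11.2 |
| 70 placebo | 4.2 | 5.6 |

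**5. Effect on the proportions.** Assume the planning rates (31%, 18%, 11%) hold in subjects with a Day 6 value, and a fraction d is missing in each arm. Counting the missing as not resolved lowers an arm's rate p by p × d:

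- SHP640: 31 × 0.06 = 1.9 to 31 × 0.08 = 2.5 points
- PVP-I: 1.1 to 1.4 points
- Placebo: 0.7 to 0.9 points

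If d is the same in both arms, the SHP640–placebo difference is 20 × 0.94 = 18.8 or 20 × 0.92 = 18.4 points, against 20 among those observed. If 8% are missing and unresolved in SHP640 only, it is 28.5 − 11 = 17.5.

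The extreme limits are (p1 − p2)(1 − d) ± d:

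| Difference | d = 6% | d = 8% |
|---|---|---|
| SHP640–placebo (20 points) | 12.8 to 24.8 | 10.4 to 26.4 |
| SHP640–PVP-I (13 points) | 6.2 to 18.2 | 4.0 to 20.0 |

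These limits require every missing subject to resolve in one arm and none in the other. They are bounds, not forecasts.

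**6. Power, for the protocol's confirmatory design only.** With all missing counted as not resolved, power is 89.4% (6%) to 88.5% (8%) for 140 vs 70, and 87.6% to 86.6% for 242 vs 242. The planning rates were observed in a study that itself had this dropout and may already include filled values, so these figures may count dropout twice.

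**The case against.** A reader might infer that the Day 6 endpoint is never measured in these subjects, or that they are barred from Visit 3. The documents do not go that far. The exit visit grades both signs and takes a swab, its date is open and could fall on or near Day 6, and nothing forbids Visit 3.

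A reader might also take LOCF to be the protocol's only answer, and an arbitrary one. Neither is right. Sensitivity imputations are promised. Resolution needs both scores at 0, so a subject withdrawn for lack of improvement will almost always carry forward a non-zero score and count as not resolved. For that group LOCF behaves much like failure imputation, which is defensible. It is less clear for subjects who stop because of intolerance while improving.

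Nor is asking for Visit 3 purely a matter of data collection. Section 4.4 foresees alternate therapy after withdrawal, and a Day 6 score taken after that credits its effect to the assigned arm. After a code break, the picture-based injection grading may no longer be masked. Using such values is a choice of estimand and has to be stated as one.

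The HSV precedent shows that attendance after a mandated stop is feasible. It does not show that subjects who leave dissatisfied would return.

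Finally, the SAP refers to protocol amendment 4.0, while the supplied protocol's history ends at Amendment 3, so the operative 4.4 is not visible. The SAP's own unmasking text and footnote b nevertheless carry the same rules.

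What stands is that Visit 3 scoring is not requested, and that the SAP has nothing to put in its place.

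**Conclusion.** The point holds as a design weakness of moderate size. A subject who stops product or is unmasked before Day 6 will usually have no Day 6 resolution or eradication value. Under the protocol that gap has a stated, partly conservative handling. Under the SAP it has none: the status is missing, no rule counts it as not resolved, and the descriptive Day 6 proportions can be biased if stopping is related to outcome or differs by arm.

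The 6% to 8% (36 to 48 of 605, or 21 to 28 of 350) is an upper limit on what could be recovered. It comes from another study, is not split by cause and includes subjects who would not return. The rise from 6% to 8% adds people with no post-baseline data at all.

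A reader might infer an invalid test or an 8-point error in an arm's rate. The SAP tests nothing, and 8 points is reached only if every dropout is a recoverable product stopper and all err in one direction. On the assumptions in step 5 of the working, counting these subjects as not resolved moves an arm's rate by about 1 to 2.5 points.

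**What to change.** In Protocol 4.4, 6.2.4, 7.1.3 and Table 1 footnote b, and in the matching SAP text:

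- Separate stopping product from leaving the study. Unless consent is withdrawn, ask subjects who stop or are unmasked before Day 6 to attend Visit 3 on its scheduled day for injection, discharge and swab, as well as the exit evaluations.
- Flag values recorded after stopping, after other treatment or after unmasking.
- Report Day 6 proportions by assigned treatment in two ways: with the observed post-stopping values, and with these subjects counted as not resolved. State in advance which is the main summary.
- Reconcile footnote b with the HSV exception in 4.4.

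None of this touches the decision to stop product or the treatment given afterwards. The cost is protocol and SAP wording, and at most one already scheduled visit for a small minority. Some values will reflect other treatment, and grading after a code break may be unmasked, which is why the flags and the second summary are needed.
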